### **13.6 Reporting and Exclusions**

Every reasonable attempt will be made to recover any missing data. If any data for the primary efficacy measure remains missing, then the change of the primary endpoint will not be calculated, and the participant will not be evaluable for the primary endpoint. We will also consider multiple imputations using predictive values based on regression models under the assumption of missing at random to supplement the primary analysis. In addition, any available data will be included in the repeated measure analysis for both primary and secondary endpoints, which allows for all participants with complete or partial data.

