#### **13.1 Study Design/Description**

A total of 198 potentially eligible participants will be consented and screened for eligibility and, with a conservative estimate, 158 (80%) participants are expected to be eligible. These 158 women will be randomized 1:1 into one of two groups: placebo or 4-OHT gel 2 mg per breast. Treatment will last for 52 weeks. Considering an attrition rate of approximately 19%, we expect to have 128 evaluable women who will have both baseline and 52-week measurements of percent MD of the breast, 64 women in each group.

With 64 women in each group, we will have an 80% power to detect a decrease of percent MD of 6% in treatment group against 2% in placebo group, with a common standard deviation of 8%, using a two-sided t-test with a significance level of 0.05. The proposed difference between the active treatment and placebo groups and the standard deviation are based on conservative estimates from the published work by Cuzick et al. The sample size calculation is performed using nQuery + nTerim 3.0.

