### 13.4 Primary Objective, Endpoint(s), Analysis Plan

The primary objective of this study is to evaluate the change in percent MD (using Cumulus software) from baseline to the week 52 in women applying 4 mg OHT gel versus placebo based on the intent-to-treat principle. The intent-to-treat population is defined as all participants who are randomized and have MD measurements from both baseline and 52 weeks. The primary analysis will be performed comparing the active group versus placebo group per randomization, regardless of the compliance of each participant.

The percent MD is the MD (percent dense area) that is visually estimated using both the mediolateral oblique (MLO) view and the craniocaudal (CC) view as the proportion of the total breast area that was composed of dense tissue (to the nearest 5%). For the study purpose, the densest breast will be the target lesion for the primary endpoint. Breast biopsy for secondary and exploratory endpoints will be performed in the opposite (non-target) breast.

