At the end of the study, all participants who have MD measurements from both baseline and 52 weeks, regardless of the compliance, will be included in the primary analysis. Change in percent MD of the breast from baseline to 52 weeks will be summarized using descriptive statistics, such as mean, standard deviation, median and range for each arm. With visual assessments of MD from both the MLO and CC views for evaluating the primary endpoint, Hotelling's  $T^2$  test will be used to conduct multivariate hypothesis testing which includes both views. Hotelling's  $T^2$  test represents the multivariate generalization to the independent two-sample t-test in the univariate setting. The correlation and variance-covariance matrix will be assessed to estimate the level of dependency between the MLO and the CC views. The mean change in percent MD at 52 weeks incorporating both the MLO and CC views will be compared between the two groups utilizing Hotelling's  $T^2$  test. Q-Q plots, used to visually assess the assumption of normality, will be constructed for the marginal distributions associated with observations emanating from both the MLO and the CC view. Assuming the mean difference in density between the observations between the 4-OHT and the placebo groups is approximately normally distributed, then the primary analysis will be conducted as previously described. Additionally, a 95% confidence ellipse (simultaneous confidence intervals) for the mean vector containing information from both views will be provided. If the change in density is not normally distributed, then we will try to rescale to achieve approximate normality by using the Box-Cox transformation. In our prior experience evaluating change in density in response to oral tamoxifen, change in density was scaled and raised to the 1.75th power to approximate normality. We will have to determine what power to use in the Box-Cox transformation based on the data that we have on hand. Transformations may be performed when necessary to make the measure of MD close to normal distribution before evaluating the change of MD over time between two groups. If the Hotelling's  $T^2$  test is significant, we will further examine whether the significant difference between the 4-OHT gel group and the placebo group is in the MLO view or the CC view or both. Note that the sample size calculation is based on the two-sample t-test. It provides a conservative estimate of the statistical power because the Hotelling's  $T^2$  test is more efficient than the two-sample t-test.

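### Read literally, Section 13.6 drops a woman from the primary test for one missing view, and Section 13.4 does not say whether a density measurement needs both views

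*Combined protocol and SAP*

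**What the plan says.** - **The measure.** Section 13.4 describes percent density as "visually estimated using both the mediolateral oblique (MLO) view and the craniocaudal (CC) view". Sections 8.1 and 13.4 take the densest breast as the target.
- **The test.** Section 13.4 compares the arms on the MLO and CC changes jointly, using Hotelling's T².
- **Who enters.** Section 13.4: "all participants who have MD measurements from both baseline and 52 weeks, regardless of the compliance, will be included in the primary analysis".
- **Missing data.** Section 13.6 first commits to recovering missing data. It then says: "If any data for the primary efficacy measure remains missing, then the change of the primary endpoint will not be calculated", and calls such a participant not evaluable for the primary endpoint. It will consider multiple imputation under missing at random to supplement the primary analysis. It also admits complete or partial data to a repeated-measures analysis of primary and secondary endpoints.
- **Sample size.** Section 13.1: "With 64 women in each group, we will have an 80% power to detect a decrease of percent MD of 6% in treatment group", against a 2% decrease on placebo, "with a common standard deviation of 8"%. It randomizes 158 women and expects 128 evaluable after about 19% attrition. Section 13.4 calls the 19% an inevaluable rate.

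No section says what happens when only one of the two views is missing.

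**The concern.** Two views at two visits make four readings. If all four belong to the primary efficacy measure, the 13.6 rule is triggered by the loss of any one. Hotelling's T² in its usual form enforces the same rule, because it needs both view changes for every woman.

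The women affected attended both visits and were imaged twice. A woman with MLO read at both visits but CC read at only one still has an observed change in the target breast, yet she contributes nothing to the primary test.

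Two things are at stake. The first is an avoidable loss of power. The second is an open choice about the primary population: 13.4 can be read as admitting her (she has a density measurement at each visit) or as excluding her (a measurement needs both views). Two analysts could build different analysis sets, and the choice could be made after the data are seen.

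**Working it through.** **1. Reproduce the plan's figure.** Inputs from Section 13.1: decreases of 6% and 2% (difference 4 points), SD 8, 64 per arm, "using a two-sided t-test with a significance level of 0.05". The noncentrality is 4 / (8 × √(2/64)) = 2.83 on 126 degrees of freedom. The exact noncentral t gives 80.1% power at 64 per arm and 79.5% at 63, so 64 is correct. Attrition: 158 × 0.81 = 127.98, or 128. The plan's figures reproduce.

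**2. Loss under the any-missing rule.** The rate of missing readings, q, is an assumption. Take 1%, 2% and 3% per reading, independent, and beyond the 19%.

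- Lost if any of four is missing: 1 − (1 − q)⁴
- Lost if one view read at both visits is enough: (1 − (1 − q)²)²
- Power: noncentral t as in step 1, at 64 × (1 − q)⁴ per arm

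| q | Lost, any of four missing | Of 128 women | n per arm | t-test power | Lost, one paired view enough |
|---|---|---|---|---|---|
| 0 | 0 | 0 | 64 | 80.1% | 0 |
| 1% | 3.9% | 5 | 61.5 | 78.5% | 0.04% |
| 2% | 7.8% | 10 | 59.0 | 76.9% | 0.16% |
| 3% | 11.5% | 15 | 56.7 | 75.1% | 0.35% |

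At q = 0.25% the loss is 1.0% of women and about 0.4 points of power (79.8%). At q = 5% it is 18.5% and 8.6 points (71.5%).

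**3. Loss if failures strike whole examinations.** If both views of a visit fail together with probability q, the loss is 1 − (1 − q)², that is 2.0%, 4.0% and 5.9% at 1%, 2% and 3%. None of it is recoverable, because no woman then has just one view missing.

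**4. The planned test.** The t-test is the plan's sizing basis, but the primary test is Hotelling's T². Further assumptions: SD 8 and a 4-point effect in each view, correlation 0.9 between the view changes.

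- Noncentrality, complete cases: λ = (n/2) × d′Σ⁻¹d, with d′Σ⁻¹d = (2 × 16) / (64 × 1.9) = 0.263. At n = 64, λ = 8.42 and power is 73.0% (F with 2 and 2n − 3 degrees of freedom).
- Available views: put r = (1 − q)². Per arm, n₂ = 64r² women have both view changes, and n₁ = 64r(1 − r) have only MLO paired, with as many having only CC paired. Each one-view woman adds 16/64 = 0.25, so λ = ½ × (0.263 n₂ + 2 × 0.25 n₁). This treats the covariance as known, so it is approximate.

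| q | T², both views complete | Joint comparison, available views |
|---|---|---|
| 1% | 71.1% (λ 8.09) | 72.9% (λ 8.40) |
| 2% | 69.2% (λ 7.77) | 72.7% (λ 8.38) |
| 3% | 67.2% (λ 7.46) | 72.5% (λ 8.35) |

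Nearly all of the power lost to single missing views comes back. With correlation 0.5 the absolute figures are higher (83.2% with no loss), and at q = 3% they are 78.0% complete-case against 81.8% with available views.

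**The case against.** - **Section 13.6 never mentions views.** True. Its phrase could mean a visit-level measurement, so the four-reading consequence is an inference. But the measure is built from both views and the test needs both changes, so a literal application gives that result, and no exception is written.
- **Partial data are already handled.** In part. A reader might infer that these women are lost to the trial. They are not: 13.6 keeps them in the repeated-measures analysis and may impute for them. Both routes are additions, though, and neither changes who enters the primary test.
- **The 19% may already cover unreadable images.** This stands. Section 13.4 calls it an inevaluable rate and reports that the current estimate is within it. A reader might add the losses above to the 19%, but the documents do not support that. If the allowance covers them, the planned 128 and 80% are unaffected, although usable readings are still set aside.
- **Independence flatters the fix.** This stands. Several failure routes in the documents act on a whole examination: deleted raw images (Sections 3 and 7.2), and unusable format or failed submission (Sections 8.1 and 10.2). The site coordinator's check and the validation step in TRIAD should also lower the rate.
- **Averaging whichever views are available would replace the planned test.** This stands. Section 13.4 treats the views as distinct and asks which one carries the effect. Any remedy should keep the joint two-view comparison.

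**Conclusion.** The point holds in a limited form. Read literally, 13.6 excludes a woman from the primary test for a single missing view, and 13.4 is ambiguous on whether one view is a density measurement.

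Two stronger readings are tempting and not supported:

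- **That 13.4 and 13.6 contradict each other.** Section 13.4 asks for density measurements, not mammograms, at both visits, and it describes the measure as using both views. The two sections can therefore be read as one complete-case rule.
- **That hard-to-image women are removed selectively, with bias.** Nothing in the documents shows loss that differs by arm. The central reader is blinded to timepoint and treatment (Section 8.1), and women who cannot be imaged in a single view are excluded beforehand (Section 4.2).

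The size is conditional. At 1% to 3% independent loss per reading beyond the 19%, power falls by 1.6 to 5.0 points on the t-test basis, or about 2 to 6 points for T² at correlation 0.9. It is smaller if failures cluster by examination, and the planned power is unchanged if the 19% already covers them. The case for acting is that the data are already collected, the rule is open to two readings, and the remedy is cheap.

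**What to change.** 1. State in 13.4 and 13.6 that a participant is evaluable for the primary endpoint if at least one view (MLO or CC) of the target breast was read at both baseline and 52 weeks, with the COVID-19 window handled as 13.4 already provides.
2. Run the primary joint comparison with a bivariate likelihood model for the MLO and CC changes: unstructured covariance, a separate treatment effect for each view, and a two-degree-of-freedom test of both effects. With complete data this is essentially Hotelling's T², so the hypothesis is unchanged.
3. Report Hotelling's T² on women with both views complete as a sensitivity analysis.
4. Report, by arm and visit, how many single views and how many whole examinations were unusable.

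**Cost.** No new data, but more than a wording change: the primary estimation method must be specified for women with one view. The model relies on missing at random for the missing view. One-view women add somewhat less information: under the step 4 assumptions 0.25 against 0.263 at correlation 0.9 (95%), and 0.25 against 0.5/1.5 = 0.333 at correlation 0.5 (75%). The change should be fixed before unblinding.

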### **13.7 Evaluation of Toxicity**

All participants will be evaluable for toxicity from the time of their first dose of 4-OHT gel 4 mg or placebo. The grade, attribution, onset and resolve date of all toxicities will be recorded and summarized for each arm and reported to the DCP monthly and to the DSMB annually as well as at the end of the study.

### **13.8 Evaluation of Response**

All participants included in the study must be assessed for response to intervention, even if there are major protocol deviations or if they are ineligible.

All of the participants who met the eligibility criteria (with the possible exception of those who did not receive study agent) will be included in the main analysis. All conclusions regarding efficacy will be based on all eligible participants.

Subanalyses may be performed on the subsets of participants, excluding those for whom major protocol deviations have been identified (e.g., early death due to other reasons, early discontinuation of intervention, major protocol violations, etc.). However, subanalyses may not serve as the basis for drawing conclusions

concerning efficacy, and the reasons for excluding participants from the analysis should be clearly reported. For all measurements of response, the 95% confidence intervals should also be provided.

### **13.9 Interim Analysis**

There is no interim analysis planned.

### **13.10 Ancillary Studies**

No ancillary studies are planned.

## **14. ETHICAL AND REGULATORY CONSIDERATIONS**

### **14.1 Form FDA 1572**

Prior to initiating this study, the Protocol Lead Investigator at the Lead or Participating Organization(s) will provide a signed Form FDA 1572 stating that the study will be conducted in compliance with regulations for clinical investigations and listing the investigators, at each site that will participate in the protocol. All personnel directly involved in the performance of procedures required by the protocol and the collection of data should be listed on Form FDA 1572.

### **14.2 Other Required Documents**

14.2.1 Current (within two years) CV or biosketch for all study personnel listed on the Form FDA 1572 and Delegation of Tasks form for the Lead Organization and all Participating Organizations.

14.2.2 Current medical licenses (where applicable) for all study personnel listed on Form FDA 1572 and Delegation of Tasks form for the Lead Organization and all Participating Organizations.

14.2.3 Lab certification (*e.g.*, CLIA, CAP) and lab normal ranges for all labs listed on Form FDA 1572 for the Lead Organization and all Participating Organizations.

14.2.4 Documentation of training in “Protection of Human Research Subjects” for all study personnel listed on the FDA Form 1572 and Delegation of Tasks form for the Lead Organization and all Participating Organizations.

14.2.5 Documentation of training in “Good Clinical Practice” for all study personnel listed on the FDA Form 1572 and Delegation of Tasks form for the Lead Organization and all Participating Organizations.

14.2.6 Documentation of Federalwide Assurance (FWA) number for the Lead Organization and all Participating Organizations.

14.2.7 Signed Investigator’s Brochure/Package Insert acknowledgement form.

14.2.8 Delegation of Tasks form for the Lead Organization and all Participating Organizations signed by the Principal Investigator and all study personnel listed on the form for each site.

14.2.9 Signed and dated NCI, DCP Financial Disclosure Form for all study personnel listed on Form FDA 1572 for the Lead Organization and all Participating Organizations.

### **14.3 Institutional Review Board Approval**

Prior to initiating the study and receiving agent, the Investigators at the Lead Organization and the Participating Organization(s) must obtain written approval to conduct the study from the CIRB. Should changes to the study become necessary, protocol amendments will be submitted to the DCP PIO according to DCP Amendment Guidelines. The DCP-approved amended protocol must be approved by the CIRB prior to implementation

### **14.4 Informed Consent**

All potential study participants will be given a copy of the CIRB and IRB-approved Informed Consent to review. The investigator will explain all aspects of the study in lay language and answer all questions regarding the study. If the participant decides to participate in the study, she will be asked to sign and date the Informed Consent document. The study agent(s) will not be released to a participant who has not signed the Informed Consent document. Individuals who refuse to participate or who withdraw from the study will be treated without prejudice.

Participants must be provided the option to allow the use of blood samples, other body fluids, and tissues obtained during testing, operative procedures, or other standard medical practices for further research purposes. If applicable, statement of this option may be included within the informed consent document or may be provided as an addendum to the consent. A Model Consent Form for Use of Tissue for Research is available through a link in the DCP website.

Prior to study initiation, the informed consent document must be reviewed and approved by NCI, DCP, the Consortium Lead Organization, and the IRB at each Organization at which the protocol will be implemented. Any subsequent changes to the informed consent must be approved by NCI, DCP, the Consortium Lead Organization's IRB, and then submitted to each organization's IRB for approval prior to initiation.

### **14.5 Submission of Regulatory Documents**

All regulatory documents are collected by the Consortia Lead Organization and reviewed for completeness and accuracy. Once the Consortia Lead Organization has received complete and accurate documents from a participating organization, the Consortium Lead Organization will forward the regulatory documents to DCP's Regulatory Contractor:

Paper Document/CD-ROM Submissions:

Regulatory Affairs Department  
CCS Associates, Inc.  
[name]  
[name]  
[contact]  
[contact]

E-mail Submissions:  
[[contact]](mailto:[contact])

Regulatory documents that do not require an original signature may be sent electronically to the Consortium Lead Organization for review, which will then be electronically forwarded to DCP's Regulatory Contractor.

#### **14.6 Other**

This trial will be conducted in compliance with the protocol, Good Clinical Practice (GCP), and the applicable regulatory requirements.

#### **15. FINANCING, EXPENSES, AND/OR INSURANCE**

Participants will not be responsible for non-standard of care costs of this study. Study agent will be provided at no cost to the participant. There will be compensation for additional expenses associated with study visits, such as additional travel expenses, time missed from work or other expenses. The amount of compensation will be \$100 associated with the Baseline study visit, Month 6 and Month 12, and \$150 at the time of each biopsy for those who agree to the procedure. Under the COVID-19 Contingency Plan, the amount of compensation will be \$100 associated with the Baseline study visit, Month 6 telephone call and Month 13-18 visit, and \$150 at the time of each biopsy for those who agree to the procedure. If, as a result of participation in this study, an individual experiences injury from known or unknown risks of the research procedures as described in the informed consent, immediate medical care and treatment, including hospitalization, if necessary, will be available. No monetary compensation is available for the costs of medical treatment for an injury, thus, the participant will be responsible for the costs of such medical treatment, either directly or through their medical insurance and/or other forms of medical coverage.

**APPENDIX A**

**Performance Status Criteria**

**ECOG Performance Status Scale**

Grade	Descriptions
0	Normal activity. Fully active, able to carry on all pre-disease performance without restriction.
1	Symptoms, but ambulatory. Restricted in physically strenuous activity, but ambulatory and able to carry out work of a light or sedentary nature (e.g., light housework, office work).
2	In bed <50% of the time. Ambulatory and capable of all self-care, but unable to carry out any work activities. Up and about more than 50% of waking hours.
3	In bed >50% of the time. Capable of only limited self-care, confined to bed or chair more than 50% of waking hours.
4	100% bedridden. Completely disabled. Cannot carry on any self-care. Totally confined to bed or chair.
5	Dead.

[figure not shown]
**Karnofsky Performance Scale**

Percent	Description
100	Normal, no complaints, no evidence of disease.
90	Able to carry on normal activity; minor signs or symptoms of disease.
80	Normal activity with effort; some signs or symptoms of disease.
70	Cares for self, unable to carry on normal activity or to do active work.
60	Requires occasional assistance, but is able to care for most of his/her needs.
50	Requires considerable assistance and frequent medical care.
40	Disabled, requires special care and assistance.
30	Severely disabled, hospitalization indicated. Death not imminent.
20	Very sick, hospitalization indicated. Death not imminent.
10	Moribund, fatal processes progressing rapidly.
0	Dead.

[figure not shown]
## Appendix B

### GEL APPLICATION INSTRUCTIONS

1. Flammable: do not apply near fire, flame or heat, or while smoking.
2. If you had a biopsy, start applying the gel at least 24 hours after the biopsy.
3. Apply the gel to your own breasts after bathing, preferably in the morning and at approximately the same time each day. Night-time application is acceptable, but caution should be taken to limit transfer to other individuals.
4. To apply, remove the cap from the bottle. When you use a bottle for the first time, you must prime it by pressing the pump fully several times until gel is dispensed (point the spout toward a sink or wastebasket and do not use the first dose, which may be incorrect).
5. Once the bottle is primed, hold it in one hand and place the palm of your other hand under the pump to catch the gel. Be sure to press down completely on the pump and release it completely to dispense one dose of gel.
6. Apply **one pump worth of gel to each breast** at one time. Do not apply more or less than this amount to each breast. Be sure to release the pump completely between actuations.
7. If you accidentally pump more than is needed for one breast, please discard this dose and try again to get the correct dose. If you do discard pumped doses, please record this on your study diary.
8. Start around the nipple. Spread outwards until you reach edge of breast bone, below collar bone (clavicle), to the fold under the breast, and to the outer edge of the breast (see picture below).

9. Do not apply to the nipple. Starting at the areola spread the gel evenly over the entire surface of your breast (see **green area** in the picture below). **Do not rub** the gel into the skin.

10. The gel should **not** be applied to any other part of the body.
11. Wash your hands with soap and water immediately after applying the gel.
12. Allow the gel on your breasts to air dry for 2 minutes and then immediately cover with clothing (the gel is colorless and will not stain your clothing). Once dry, the gel is no longer flammable. Do not expose your bare breasts to sunlight at any time.
13. Do not apply any other cream, lotion or moisturizer to your breasts for at least 4 hours following application of the study gel. If cream, lotion, or moisturizer is used between applications, wash the breast skin before applying the next dose.
14. Do not wash your breasts or immerse in water (bath, swim) for at least 4 hours following application of the gel. If this is not possible, delay application of the gel that day until after immersion, and be sure to follow all the above instructions. If you regularly swim in the morning, it is better to apply the gel afterwards, after your shower.
15. After use, replace the cap on the bottle.
16. Avoid exposure of the treated breast skin to natural or artificial sunlight. This includes sunbathing or the use of tanning beds with the breasts exposed. Also, if you have dermatologic conditions causing the breakdown of skin in the area of gel application, you should not use 4-OHT gel.

